5.4 Unscheduled Visits

5.4.1 Subjects Meeting the Influenza-Like-Illness Criteria

Clinic Visit or Home Visit – Obtaining NP Swab

Subjects will be asked to come to the site for an unscheduled clinic visit when experiencing symptoms meeting the primary protocol-defined ILI criteria. Subjects will be reminded to bring their ILI booklet. In the exceptional case that a clinic visit is not feasible, a home visit may be considered. The visit should occur as soon as possible, preferably within 3 days, and up to 6 days following onset of protocol defined ILI symptoms. During the visit the following procedures should be carried out:

- Assess ILI symptoms and assess associated medication. Document any anti-viral medication use from the first day of onset of ILI symptoms.
- Collect a NP swab for evaluation of the presence of influenza virus following the procedures for collecting, processing and shipping as described in the Lab Manual.
- Evaluate the subject's body temperature (preferably oral), heart rate, respiratory rate and blood pressure and perform a symptom-directed physical examination.
- Record the ILI, related information, medically-attended adverse events from ILI onset and associated concomitant medication in the source documents and in the eCRF (ILI-report and adverse events section).
- Schedule in next study activity and hand out new ILI booklet.

ILI Follow-up Safety Call

An ILI follow-up safety call will be performed at 30 (+7) days after primary protocol-defined ILI onset, amongst subjects who have had their NP swab obtained

During the visit the following procedures should be carried out:

- Assess ILI symptoms and associated medication, if any.
- Assess for medically-attended adverse event.
- Remind subject of next study activity.

5.5 Study Termination Visit

The study termination phone call will occur on Day 181 (“previously vaccinated” subjects) or Day 209 (“not previously vaccinated” subjects, or until the end of influenza season, whichever is longer). The termination visit consists of a telephone call. The date of termination is the date of the last contact (telephone call) in which the subject’s health status was assessed or, in cases where the subject and/or parent/legal guardian does not agree to any further safety follow-up, it is the date consent is withdrawn. This date should be recorded on the termination CRF page. For visit procedures to be performed for a subject whose planned study participation ends prematurely, please see [Section 5.5.1, Early Termination Visit](#).

At the termination phone call, the following procedures will be performed:

- Interview the subject to obtain information regarding potential SAEs, ILIs, NOCDs, AEs leading to withdrawal and the medication to treat these.
- Ask the subject or parent/legal guardian as to whether the subject was hospitalized or was evaluated at an emergency room for any illness since the site’s last contact with the subject. If an SAE has been identified by the site staff during the interview and has not previously been reported by the subject, this SAE must be reported by the site within 24 hours to Seqirus or delegate. Record any additional relevant medical history as needed.

Potential ILI symptoms will be documented in the subject’s source records. If the onset of the ILI is 3, or at most 6, days before the visit, an NP swab should be collected from the subject for influenza testing and study staff will document the ILI on an Adverse Event and ILI CRF. See procedures described in [Section 5.4.1](#). Should an ILI be identified, it is recommended to postpone the study termination visit, to allow for the ILI follow-up visit to occur.

- Should the subject have experienced a protocol defined ILI for which an NP swab was obtained, please ensure collection and review of the ILI booklet and collect the information of any medically-attended adverse events which have occurred within 30 days after the onset of the of ILI.
- A qualified healthcare professional will perform a brief symptom-directed physical examination if necessary according to symptoms the subject has reported. This is a physical examination that will include an examination of organ systems that are relevant to the investigator based on review of the subject’s reported adverse events, concomitant medication use. This assessment may include: measurement of vital signs (respiratory rate, blood pressure and heart rate), body temperature (preferably oral) and a check of general appearance. The physical assessment must be performed by the investigator or designee of the investigator, who is qualified to perform a physical

assessment in accordance with their institutional policy. Measurement and recording of vital signs and body temperature may be conducted by a trained health care professional. Corresponding information is documented in the subject's source document and eCRF(s). Measurement and recording of vital signs and body temperature may be conducted by a trained health care professional.

The site will review with the subject/subject's parent(s)/legal guardian(s) the plan of when information relating to the subject's participation in the study may be available (e.g., study results, treatment assignments). It will also be discussed how information relating to the subject's participation in the study will be shared with the subject's healthcare provider, if the subject/subject's parent(s)/legal guardian(s) chooses to share this information.

The site will complete the termination eCRF page and this will mark the completion of the subject's participation in the study.

5.5.1 Early Termination Visit

When a subject is withdrawn from treatment or withdraws from the study, the investigator will notify the Sponsor and, when possible, will perform the procedures listed below. The reason(s) for the early termination will be included in the subject's source documentation. If the Early Termination Visit is a telephone call, collect as much information as possible. Early Termination Visits include subjects who were randomized but not treated.

At the clinic visit or during the telephone call, the same procedures will be performed as during the study termination visit, see [Section 5.5, Study Termination Visit](#), if possible.

In addition, the following procedures will be performed:

- Collect and review Subject Diary, if applicable.
- Review the subject's safety data (if collection of these was in progress at the time of study termination).
- Collect and review ILI booklet, if applicable.

The site will review with the subject/subject's parent(s)/legal guardian(s) the plan of when information relating to the subject's participation in the study may be available (e.g., study results, treatment assignments). It will also be discussed how information relating to the subject's participation in the study will be shared with the subject's healthcare provider, if the subject/subject's parent(s)/legal guardian(s) chooses to share this information.

The site will complete the termination eCRF page and this will mark the completion of the subject's participation in the study.

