3.8 Premature Withdrawal from Study

Subjects may withdraw at any time, or be dropped from the study at the discretion of the investigator should any untoward effects occur and/or for safety reasons. In addition, a subject may be withdrawn by the investigator or the Sponsor if he/she violates the study protocol and related procedures or for administrative reasons. The investigator or study coordinator must notify the Sponsor immediately when a subject has been withdrawn due to an adverse event.

The circumstances above are referred to as premature withdrawal from the study, and the reason for premature withdrawal should be clearly documented and detailed in the source documentation. The investigator should make every attempt to evaluate the subject's safety, including resolution of ongoing AEs, at the time of premature withdrawal. If a subject want to withdraw from the study before all doses are administered or prior to the last planned study visit, the subject will be asked to be followed for safety for the duration of the study. When a subject withdraws, or is withdrawn, from the study, the procedures described in [section 5.5.1, Early Termination Visit](#) should be completed if possible.

The reasons for premature withdrawal from the study include:

- Adverse event,
- Death
- Withdrawal of consent
- Lost to follow-up
- Administrative reason
- Protocol deviation
- Other

These reasons are described in greater detail below.

Adverse Event

For any subject withdrawn from study participation prior to the planned Study Termination Visit, it is important to determine if an AE was associated with the reason for discontinuing the study. This AE must be identified on the AE CRF page by indicating "Withdrawn from study due to AE". Any ongoing AEs at the time of study withdrawal must be followed until resolution or stabilization.

Subjects who develop a serious adverse event (SAE) judged to be possibly or probably related to the study vaccine, including hypersensitivity reactions, should not receive subsequent vaccination.

If a medically attended adverse event occurred within 30 days following a primary protocol definition of ILI, the event should also be reported on the AE eCRF page.

Death

For any subject withdrawn from study participation due to death, this should be noted on the Study Termination CRF page and the associated SAE that led to the death must be reported.

Withdrawal of consent

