If the clinical study is prematurely terminated by the Sponsor, the investigator is to promptly inform the study subjects and local EC/IRB and should assure appropriate therapy and follow up for the subjects. All procedures and requirements pertaining to the archiving of study documents should be followed. All other study materials (study medication/vaccines, etc.) must be returned to the Sponsor.

For subjects who are withdrawn from the study due to receipt of an excluded medication/vaccination or due to significant protocol non-compliance, this reason should be noted in the Study Termination CRF page. A subject (or legal guardian) is considered to be compliant if the Investigator judges that the subject will complete the Subject Diary when applicable, return for all the follow-up visits, and be available for telephone calls as scheduled.

Protocol Deviation

A protocol deviation is any change, divergence, or departure from the study design or procedures of a study protocol. In general, subjects associated with protocol deviations may remain in the study unless continuation in the study jeopardizes the subject's health, safety, or rights.

Investigators will apply due diligence to avoid protocol deviations. Under no circumstances should the investigator contact Seqirus or its agents, if any, monitoring the study to request approval of a protocol deviation, as no authorized deviations are permitted. If the investigator feels a change to the protocol would improve the conduct of the study this must be considered a protocol amendment, and unless such an amendment is agreed upon by Seqirus and approved by the IRB/EC and health authorities it cannot be implemented.

Any subject who becomes pregnant during the study, despite the protocol requirement for adequate contraception, will not receive further vaccination(s) but should be encouraged to continue participating in the study for safety follow-up. The site must complete a paper Pregnancy Report form (initial report) as soon as possible after learning of pregnancy occurrence (see [section 7.1.6, Pregnancies](#) for further details). If the pregnant subject withdraws from the study for any of the above categories except death, the site will obtain permission from the subject to continue to remain in contact with her until the outcome of the pregnancy is known, even if the outcome is not known until after the subject reaches the end of follow-up period.

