4.4 Criteria for Repeat Vaccination in the Study

Prior to receipt of second study vaccination (“not previously vaccinated” subjects), subjects must be evaluated to confirm that they are eligible for subsequent vaccination. If subjects meet any of the original exclusion criteria (except for those listed under [Section 4.3](#)) or the criteria listed below, they should not receive additional vaccinations.

- Subjects who experience any SAE judged to be related to study vaccine including hypersensitivity reactions.
- Subjects who develop any new condition which, in the opinion of the investigator, may pose additional risk to the subject if he/she continues to participate in the study.

Subjects who meet any of these criteria must not receive further study vaccinations. However, these subjects should be encouraged to continue study participation, as discussed in [Section 3.6](#).

There are also circumstances under which repeat vaccination is a contraindication in this study. These circumstances include anaphylaxis or severe hypersensitivity reactions following vaccination. If these reactions are to occur, the subject must not receive additional vaccinations but is encouraged to continue in study participation.

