6.5 Prior and Concomitant Medications and Vaccines

Data on medications including any vaccinations that were taken by the subject up to 2 months prior to enrollment will be recorded in the source documents and collected on the relevant Prior and Concomitant Medications eCRF. Data on influenza vaccinations that were administered to the subject up to 6 months prior to enrollment will be recorded in the source documents and collected on the Prior and Concomitant Medications eCRF.

When recording prior and concomitant medications/vaccinations, these should be checked against the study entry and continuation criteria in [Sections 4.1](#) through [4.3](#) to ensure that the subject should be enrolled/continued in the study.

The use of antipyretics and/or analgesic medications within 24 hours prior to vaccination must be identified and the reason for their use (prophylaxis versus treatment) must be described in the source documents and/or diary card and Concomitant Medications eCRF.

Medications taken for prophylaxis are those intended to prevent the onset of symptoms. Medications taken for treatment are intended to reduce or eliminate the presence of symptoms that are present.

From study entry through termination, concomitant medications will be recorded in the Concomitant Medications eCRF as outlined below:

- All medications, with the exception of vitamins and minerals, will be recorded beginning from the time of vaccination and continuing for 21 days following each vaccination received.
- Medications associated with SAEs, AEs leading to study withdrawal, NOCDs, and all vaccinations will be recorded from Day 1 to Day 181, or until the end of influenza season whichever is longer, for “previously vaccinated” subjects and from Day 1 to Day 209, or until the end of influenza season whichever is longer, for “not previously vaccinated” subjects.
- All medications associated with any medically-attended adverse events within 30 days after the ILI onset

The following treatments, if used within the Treatment Period (Day 1 through 3 weeks following subject’s last study vaccination only), e.g., in case of a medical need, represent a protocol deviation and may result in the subject being excluded from the Per Protocol Set (PPS):

- Cancer chemotherapy.
- Immunosuppressive agents or systemic corticosteroids at any dose (topical, inhaled, and intranasal corticosteroids are permitted). A single dose of intra-articular corticosteroids is also permitted).

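### Protocol 5.5.1 ends study participation for a child who only stops vaccination, in conflict with 4.4, 3.8 and 5.5, so sites could stop influenza surveillance in children the primary analysis still includes

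*Protocol*

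**What the plan says.** Protocol 5.5.1 (Early Termination Visit) has two triggers, stopping treatment and leaving the study: "When a subject is withdrawn from treatment or withdraws from the study, the investigator will notify the Sponsor". After one common list of procedures it closes the record: "The site will complete the termination eCRF page and this will mark the completion of the subject's participation in the study". There is no exception for a child who only stops vaccination.

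Protocol 4.4 (Criteria for Repeat Vaccination in the Study) covers children who may not receive dose 2. It bars further vaccination, then adds: "However, these subjects should be encouraged to continue study participation". It repeats this for anaphylaxis and severe hypersensitivity.

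Protocol 3.8 (Premature Withdrawal from Study) sends a subject to 5.5.1 on withdrawal from the study. For a subject who wants to leave before all doses are given, it says "the subject will be asked to be followed for safety for the duration of the study". Protocol 5.5 points to 5.5.1 only when planned participation ends early.

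The Synopsis (Study Design) and Protocol 3.1 run the weekly ILI contacts to the end of the influenza season or to early discontinuation. SAP 7.3 admits to the efficacy FAS any child with at least one dose who is evaluated for efficacy from 14 days after the last vaccination, analysed as randomised. SAP 11.1 bases the primary and co-primary analyses on that set and right-censors subjects who drop out.

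**The concern.** Stopping vaccination and leaving the study are different events, and the primary analysis depends on keeping them apart. A child who receives dose 1 and not dose 2 remains in the efficacy FAS. Follow-up of that child for influenza to the end of the season is what the as-randomised comparison needs.

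Read literally, 5.5.1 ends that follow-up. The weekly contacts are what prompt the swab visit (Protocol 5.3.3), and swabs are not taken later than 6 days after ILI onset (Protocol 7.2). Once the contacts stop, later influenza in that child is unlikely to be confirmed, and the child is censored.

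The censoring may not be independent of outcome or arm. Under 4.4 the reasons for withholding dose 2 include a vaccine-related SAE or hypersensitivity after dose 1, and dose 1 is QIVc in one arm and Men ACWY in the other. They also include meeting an original exclusion criterion, one of which is recently documented influenza. In addition, a site working from 4.4 and a site working from 5.5.1 would handle the same child differently.

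**Working it through.** **1. The passages side by side**

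- *When 5.5.1 applies.* By its own text: stopping treatment, or leaving the study. By 3.8: leaving the study. By 5.5: participation that ends early.
- *What follows for a child who only stops vaccination.* By 5.5.1: the termination form, and participation is complete. By 4.4: the child is encouraged to stay. By the pregnancy rule in 3.8: no further vaccination, and continued participation for safety follow-up is encouraged.
- *Does a cross-reference settle it?* No. Section 4.4 cites 3.6 for continued participation, but 3.6 holds the stopping and pausing guidelines and gives no follow-up instruction for these children.
- *Do weekly ILI contacts continue?* The Synopsis and 3.1 stop them at early discontinuation, without saying whether that means discontinuing vaccination or the study. Section 5.3.3 gives season end only. Neither 4.4 nor 3.8 mentions the weekly contacts.

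**2. One child traced through the plan**

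A not previously vaccinated child receives dose 1 on Day 1 and is barred from dose 2 at the Day 29 visit (window ±3 days).

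- Following 4.4: surveillance continues to season end, and the child contributes full time at risk.
- Following 5.5.1: the record closes at about Day 29. If last vaccination means the last dose received, cases count only from more than 14 days after Day 1, that is, after Day 15. Time at risk is then about 29 − 15 = 14 days (11 to 17 with the visit window), followed by censoring.

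A child terminated before that risk period starts may not enter the FAS at all.

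**3. How many children could be affected**

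The documents state no figure for this, so there is none to reproduce. The inputs are the two-dose stratum of 2,044 to 2,860 children and total enrolment of 7,692 (Protocol Table 3.1.1).

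- Share of enrolment with a second dose to miss: 2,044 / 7,692 = 26.6%; 2,860 / 7,692 = 37.2%.
- The proportion missing dose 2 is not given. I assume 1% to 10%, with every such child terminated under 5.5.1.
- Low end: 2,044 × 0.01 = 20 children, or 20 / 7,692 = 0.3% of enrolment.
- High end: 2,860 × 0.10 = 286 children, or 286 / 7,692 = 3.7% of enrolment.

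These are upper limits for each assumed rate. Children who miss dose 2 because consent was withdrawn or contact was lost would be lost under any wording.

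**4. Would the SAP's missing-data rule pick this up?**

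SAP 8.2.3 examines the missingness mechanism only when 20% or more of subjects lack efficacy data. Even the high end, 3.7% of enrolment, is far below 20%. A child censored early may not count as missing under that rule at all.

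**The case against.** The strongest reply is that this is one loose phrase against consistent specific text. Section 4.4 says twice that these children stay, and 5.2.2 sends the site to 4.4 at the Day 29 decision. Sections 3.8 and 5.5 reserve 5.5.1 for study withdrawal or early end of participation. Section 5.5.1 itself covers subjects randomised but not treated, whom 5.1.4 classes as early terminations, so its reference to treatment may have been aimed at them. Much of this stands: many sites would probably do what 4.4 says. But 5.5.1 is the instruction for completing the form that ends participation, and nothing in it limits the treatment trigger to never-treated subjects.

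A reader might also infer more than the documents support.

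- *That 3.8 and 6.5 conflict over excluded medication.* Section 3.8 speaks of subjects "withdrawn from the study due to receipt of an excluded medication/vaccination or due to significant protocol non-compliance", but as an instruction on what to record for those who are withdrawn. Elsewhere 3.8 makes such withdrawal discretionary and says subjects with deviations may generally remain. Section 6.5 says these treatments "represent a protocol deviation and may result in the subject being excluded from the Per Protocol Set" and does not say whether the child is still followed. The two can be read together.
- *That 3.8 gives up ILI capture.* It lets a family continue with a subset of procedures, and the scheduled safety calls ask about ILI (5.3.2). What it leaves unstated is the weekly contacts, and two safety calls cannot replace these given the 6-day swab limit.
- *That SAE and NOCD follow-up is cut short in children who reacted to dose 1.* Sections 3.8 and 4.4 ask for the opposite. It follows only from a literal reading of 5.5.1.
- *That the trial loses a material number of cases or power.* The miss rates are assumed. The 381-event target is for ages 3 and over, while the two-dose stratum includes 2-year-olds. The trial is event-driven and can be extended, and about 10% dropout is already allowed for. As a bound, the Schoenfeld formula for VE 50% against 30% needs 4 × (1.960 + 1.282)² / ln(0.50/0.70)² = 372 events, close to the stated 381, at which power is 90.7%. Removing 286 × 6% = 17 events without replacement would leave 89.4%.

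**Conclusion.** The inconsistency is real, is in the current text, and is not resolved elsewhere in the documents. A site that follows 5.5.1 literally would close the record of a child whom 4.4 wants kept and whom the efficacy FAS includes. The cost is avoidable, possibly informative censoring and uneven handling across sites; it is not a power problem.

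The size is modest and uncertain: at most about 20 to 286 children, assuming that 1% to 10% of the two-dose stratum miss dose 2 and that every one of them is terminated. The documents supply neither quantity and give no evidence that the loss would differ by arm. That possibility rests on dose 1 being a different product in each arm and on 4.4 tying the loss of dose 2 partly to reactions to dose 1. The point should be corrected because the correction is cheap and the SAP's missing-data rule would not reveal the loss.

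**What to change.** Reconcile 5.5.1 with 4.4, 3.8 and 5.5:

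- Limit 5.5.1 to withdrawal from the study, including subjects randomised but not treated.
- Record the end of vaccination, with its date and reason, separately from the end of participation.
- State in 4.4 and 3.8 that weekly ILI contacts, swabs and safety calls continue as scheduled after vaccination stops, unless consent for them is withdrawn.
- Correct the pointer in 4.4 to Section 3.6, and say in the Synopsis and 3.1 that early discontinuation of the ILI contacts means leaving the study.

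No change is proposed to who may receive dose 2, or to the investigator's and sponsor's discretion over withdrawal in 3.8.

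The cost is a wording amendment, a site memo, and a separate entry for the end of vaccination if the eCRF does not already hold one. The contacts and swabs are already planned for these children, so no study procedure is added.
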